not testable, but we can look at the variables that were observed in groups with and without missing outcomes data. No association between observed variables and the group (missing vs. no missing) will be considered an indication that the data are missing at random. In addition, we will look at the reported reasons for missing values when available. If we can assume data are missing at random, we will use multiple imputation procedures. If there appear to be non-random missing outcomes data, we will use two methods designed to account for this: Heckman's selection models and pattern-mixture models, both of which model the joint distribution of the outcome and the missing mechanism. In the case of non-ignorable missing data, we will use both methods as a sensitivity analysis. If less than 5% of the data is missing and we can assume ignorable missing data, the following analysis will be performed.

Hypothesis 1 states that Veterans randomly assigned to receive eight group sessions of HYP or MM will report significantly greater pre- to post-treatment decreases in average pain than Veterans receiving eight sessions of ED. The response variable will be change in average pain intensity score from pre- to post-treatment (Pre-treatment score – Post-treatment score). This response variable will be analyzed using an analysis of covariance (ANCOVA) with treatment condition (HYP, MM, ED) as the explanatory variable and the baseline pain as a covariate.

Support for Hypothesis 1 would emerge if a significant treatment main effect is present after adjusting for the baseline covariate, and subsequent post-hoc analyses indicate larger baseline to post-treatment decreases in pain intensity in the HYP and MM conditions, relative to the ED condition. The overall significance level for the test of the null hypothesis that all three treatments have equal effect will be set to 0.05.

Although we anticipate that HYP and MM will have similar effects on the primary outcome variable, these analyses will also allow us to compare the relative effects of HYP and MM with each other, as part of the exploratory aims/analyses.

Pairwise comparisons of the treatment groups will be performed using Tukey method (see for example, Analysis of Messy Data Volume 1: Designed Experiments, Second Edition, by GA Milliken and DE Johnson. 2009, chapter 3).

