Power to test the primary study hypothesis. The primary study outcome variable is change in average pain intensity, as represented by the difference between the baseline and post-treatment average pain intensity measures. We have used this measure successfully in numerous previous trials.^{41, 42, 52, 105, 106} Anticipated effects for HYP are based on the changes observed in our previous HYP trials using the 0-10 NRS measure, plus our pilot study of HYP for low back pain treatment, reported in the

'Preliminary findings' section.

Anticipated effect sizes for MM are based on published studies of the effects of treatments that involve mindfulness that used 0-10 NRS measures.

Assuming a decrease in pain score of 0.3 points for the education group, 0.8, 1 and 1.4 for the HYP, and 0.6, 0.8 and 1 for MM, we calculated the sample size to find differences between pre-post treatment difference scores, with an alpha of 0.05, power of 0.80, and varying the standard deviation (SD) from 0.15 to 1 (to cover values observed) when using an ANOVA. Sample sizes of 80 completers per condition (total = 240) will have at least 80% power, even at the largest standard deviation.

Power for secondary and exploratory analyses.

The sample size calculations above take into consideration only the primary hypothesis of interest (that different treatment have different effects in changing pain intensity), which is the most important result this study can provide for the person affected with chronic pain. However, the sample size of this study is relatively large and will provide extremely useful and important information regarding secondary outcomes, mediators and moderators associated with pain intensity and EEG. The results will form the basis for continuing research not only to find treatments that are efficacious, but also to hypothesize mechanisms of action, which will be crucial in designing future studies.

Power Calculations (Sub-Study)

We focus our power calculations on the most innovative aspect of the supplemental study, that is, the objective measurement of sleep by means of wrist actigraphy in the context of non-pharmacological pain treatments.

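### A cheap gain in power: with three arms, Tukey after a significant omnibus F is stricter than the plan's 5% family-wise target requires

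*Combined protocol and SAP*

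**What the plan says.** D6x (Statistical Analyses, Main Study, Hypothesis 1) defines success in two steps. The rule opens: "Support for Hypothesis 1 would emerge if a significant treatment main effect is present after adjusting for the baseline covariate, and subsequent post-hoc analyses". Those post-hoc comparisons must then show "larger baseline to post-treatment decreases in pain intensity in the HYP and MM conditions, relative to the ED condition". The level of the first step is fixed: "The overall significance level for the test of the null hypothesis that all three treatments have equal effect will be set to 0.05". For the second step the section says "Pairwise comparisons of the treatment groups will be performed using Tukey method" and cites a textbook chapter. The same section says that the analyses will also "compare the relative effects of HYP and MM with each other, as part of the exploratory aims/analyses". So two pairs carry the hypothesis and the third does not.

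D6z (Power Analyses) sizes the trial for the three-group ANOVA only: 80 completers per arm, alpha 0.05, at least 80% power at the largest SD considered. It gives no power for the comparisons with ED.

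**The concern.** The trial's answer lies in two contrasts, HYP vs ED and MM vs ED. Under D6x each must clear a threshold set for three pairs, after the omnibus test has already been passed. If the omnibus step and ordinary pairwise tests together hold the family-wise error at 5%, Tukey gives up power that the design already has. The weaker arm would lose most, and D6z assumes throughout that this may be MM.

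**Working it through.** **Inputs.** From D6z: "Assuming a decrease in pain score of 0.3 points for the education group, 0.8, 1 and 1.4 for the HYP, and 0.6, 0.8 and 1" (the last three values belong to MM); SD of the change score 0.15 to 1; 80 completers per arm; alpha 0.05. From D6x: F at 0.05, then Tukey on all pairs. Tukey is read as the usual studentised-range comparison of three means. Residual df = 240 − 3 = 237.

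**1. The plan's own figure.** Least favourable case: decreases 0.3, 0.8 and 0.6, SD 1. The mean is 0.567 and the squared deviations sum to 0.0711 + 0.0544 + 0.0011 = 0.1267. The noncentrality is 80 × 0.1267 / 1² = 10.13. The critical F(2, 237) is 3.034 and power is 81.6%. The stated figure of at least 80% reproduces.

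**2. Why F followed by unadjusted tests is enough.** With three means, any two pairwise equalities imply the third. So either all three means are equal, or exactly one pair is, or none is. If all are equal, a false claim requires a significant F, which has probability 5%. If one pair is equal, only one false claim is possible, and its test has level 5%. The family-wise error is therefore at most 5% in every case. This argument is specific to three groups.

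**3. Thresholds.** The unadjusted critical |t| is 1.970. Tukey's is q/√2 = 2.359, a per-pair p below 0.0192.

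**4. Family-wise error (simulation, 80 per arm).**

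| Truth | F then Tukey | Tukey alone | F then unadjusted t |
|---|---|---|---|
| All arms equal | 4.5% | 5.0% | 5.0% |
| One arm differs | 1.9% | 1.9% | 5.0% |

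**5. Power at SD 1.** The standard error of a difference is √(2/80) = 0.158. A 0.3-point difference is therefore 1.90 standard errors, and a 0.5-point difference 3.16. Each cell gives the plan, then the closed procedure.

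| HYP / MM decrease | HYP vs ED | MM vs ED | Both | At least one |
|---|---|---|---|---|
| 0.8 / 0.6 | 78% / 81% | 32% / 46% | 30% / 45% | 80% / 81% |
| 0.8 / 0.8 | 79% / 86% | 79% / 86% | 67% / 80% | 90% / 91% |
| 1.0 / 0.8 | 98% / 98% | 79% / 88% | 78% / 88% | 98% / 99% |
| 1.4 / 1.0 | 100% / 100% | 98% / 99% | 98% / 99% | 100% / 100% |

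**6. Range.** Over all nine pairs of means, at eleven SDs from 0.15 to 1, the largest losses are 15.4 points for MM vs ED, 15.5 for both, 9.2 for HYP vs ED and 1.6 for at least one. The first two maxima occur at SD 0.9 with MM at 0.6. At SD 0.5 and MM 0.6, MM vs ED has 92.3% against 96.5%, a loss of about 4 points.

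**7. Which step costs the power.** In the 0.8 / 0.6 case at SD 1, Tukey without the F gate gives 79% for HYP vs ED and 32% for MM vs ED, against 78% and 32% with it. Over the whole grid the gate costs Tukey at most 1.1 points. Nearly all of the loss comes from using Tukey where unadjusted tests would do.

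**The case against.** An omnibus ANCOVA followed by Tukey is conventional, prespecified and referenced, and it controls the family-wise error. All of that stands: this is a choice about efficiency.

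A reader might infer that two stacked corrections cause the loss, so that dropping the F gate would cure it. Step 7 shows otherwise; the gate costs about 1 point at most.

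A reader might also infer that Tukey buys no error control at all. It does buy some: with one effective arm the error is 1.9%, against 5.0% under the closed procedure. The supportable statement is that this goes beyond a 5% target. Tukey also offers simultaneous intervals for all three pairs, which has some value because HYP vs MM will be described. D6x does not ask for such intervals.

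The size can be overstated too. Fifteen points applies to the 0.3-point MM contrast, or to winning on both arms, at an SD near 1. The SD in D6z is for the unadjusted change score; the ANCOVA residual SD is not given, and if it is smaller the loss changes.

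Timing is the most serious practical objection. The timeline in D2 ends data acquisition in April 2019, the analysis text was revised in May 2019, and the current version is dated June 2020. Relaxing a primary threshold that late needs care. The documents do not show whether outcomes had been seen by arm.

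**Conclusion.** The point holds as a low-cost improvement. The planned rule is valid but runs below its own 5% family-wise target. On the D6z assumptions at SD 1, it lowers the chance that both active arms beat ED from 45% to 30% in the least favourable case, and from 80% to 67% when both arms improve by 0.8. The chance that at least one arm succeeds barely changes. With large effects or a small SD the loss is slight.

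These figures assume 80 analysed per arm, normal outcomes with equal variances, and the change-score SD in place of the unknown ANCOVA residual SD. The closed-test argument in step 2 does not depend on the means or the SD.

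The documents do not support reading this as an error in the primary analysis. Nor is there a need to carry the change to the secondary outcomes: D6x labels those analyses exploratory, and for the comparison of group means there it asks only for pairwise post-hoc tests.

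**What to change.** For the primary outcome only, replace the Tukey sentence in D6x with: *If the omnibus treatment effect is significant at 0.05, HYP-ED and MM-ED (and, as exploratory, HYP-MM) will each be tested from the ANCOVA at two-sided 0.05; with three arms this closed procedure controls the family-wise error at 5%.*

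The change alters the rejection rule, so it should be made, dated and justified before anyone sees outcomes by arm. If that point has passed, keep Tukey as the primary rule and report the closed procedure as supplementary.

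No participants or measurements are added. The statistical cost is that the pairwise 95% intervals are no longer simultaneous. If simultaneous intervals against ED matter more, Dunnett without the F gate (critical |t| 2.224) provides them but recovers only part of the loss: in the 0.8 / 0.6 case at SD 1 it gives 37% for MM vs ED and 35% for both.

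The same edit should settle whether success means one active arm or both. The hypothesis joins the arms with *or*, the support rule with *and*. If both must beat ED, each contrast can be tested at 0.05 with neither adjustment nor gate (45% for both in the same case).

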Two such skills-based self-management techniques that may contribute to better pain management and improvements in psychological functioning and sleep quality in Veterans are self-hypnosis (HYP) and mindfulness meditation (MM). Both HYP and MM are easily taught and learned, and therefore could be seamlessly incorporated into clinical practice in VA hospitals and clinics across the country. However, *at this point in time, little is known about the efficacy of HYP and MM interventions for chronic pain in Veteran populations, their effects on co-morbid conditions, and their biological and psychological mechanisms.* Such information is critical to the development of strategies to efficiently and cost-effectively maximize their efficacy and to ensure optimal implementation.

The purpose of this randomized controlled trial is to test the efficacy and mechanisms of HYP and MM on chronic pain in 240 Veterans. Participants will be randomly assigned to 8 group sessions of (1) HYP, (2) MM, or (3) an education control condition (ED). Primary (characteristic pain intensity) and secondary outcomes will be assessed at pre-treatment, three times during treatment, post-treatment, and at 3- and 6-month follow-up. Potential treatment moderators and mediators will also be assessed.

The study will address two aims.

Aim 1: Determine the efficacy of 8 sessions of group delivered HYP and MM training for reducing characteristic pain intensity in Veterans, relative to 8 sessions of ED. The hypothesis associated with Aim 1 is:

Hypothesis 1: *Primary Study Hypothesis.* Veterans receiving 8 sessions of HYP or MM training will report significantly greater pre- to post-treatment decreases in average pain intensity than Veterans receiving 8 sessions of ED.

Aim 2: Evaluate the moderation effects of brain states (as measured by EEG) on response to HYP and MM, relative to ED. The hypothesis associated with Aim 2 is:

Hypothesis 2: *Brain State Moderating Hypothesis (Secondary)*. Pain reduction with HYP and MM will be significantly associated with different patterns of baseline brain activity. Specifically, participants who report the most pain reduction with HYP will evidence higher levels of global theta activity and lower levels of left frontal gamma activity at baseline. Participants who report the most pain reduction with MM will evidence lower levels of alpha activity at baseline. Baseline brain activity will not be significantly associated with pain reduction following ED.

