Addressing Aim 2 by testing Hypothesis 2. Hypothesis 2 states that baseline EEG activity will predict differential response to HYP and MM, such that those participants who have higher baseline levels of global theta, and lower baseline levels of left frontal gamma will respond to HYP, while participants with lower baseline levels of global alpha will respond to MM. We will test for this moderator using a linear regression analysis, with pre- to post-treatment change in pain intensity as the response (criterion) variable. Treatment Condition, absolute power of baseline theta, alpha, and (left frontal) gamma, and terms representing the interaction between treatment condition and each EEG bandwidth will be the explanatory variables. Significant Treatment Condition X Theta, Alpha, and Gamma interactions, with higher coefficients for baseline theta and lower coefficients for baseline gamma in the HYP group, and lower coefficient for baseline alpha in the MM group would support Hypothesis 2.

Additional exploratory analyses. In addition to testing the two study hypotheses, we propose a series of exploratory analyses (explained below) to take full advantage of the data collected to better understand the effects and potential mechanisms of HYP and MM. However, because these analyses are exploratory, we will report them as such. Any statistically

significant findings will be viewed as providing support for further, more definitive, testing in the future.

Effects of HYP and MM on secondary outcomes. To examine the potential effects of HYP and MM, relative to ED, on co-morbid conditions, we will repeat the ANCOVA analyses planned to test Hypothesis 1 for the secondary outcome variables (assessing pre- to post-treatment decreases in depression, anxiety, sleep disturbance, pain interference, PTSD symptoms) as the response variables, controlling for the respective baseline measures of these secondary outcomes. The response variable will be change in each outcome measure score from pre- to post-treatment (Pre-treatment score – Post-treatment score). This response variable will be analyzed using an analysis of covariance (ANCOVA) with treatment condition (HYP, MM, ED) as the explanatory variable and the corresponding baseline value for each secondary outcome measure as a covariate.

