Perceived global improvement is a secondary outcome measure but unlike the other secondary outcome measures it was not measured at baseline, hence a slightly different approach will be used for this secondary outcome measure. Instead of a change score, we will simply use ANOVA to compare perceived global improvement with treatment condition as the independent variable.

To assess the effect of each treatment on post-treatment ratings of global satisfaction (which has only 5 categories), we will use an ordinal polytomous logistic regression. Because we anticipate that *both* HYP and MM will have significant beneficial effects on outcomes, we do not anticipate large differences between these two interventions in the outcome measures. However, we think that it would be important to estimate differences in outcome between the two active treatments for descriptive purposes. To do so, we will perform pairwise post-hoc tests to compare the means of the three groups.

We will report both the p-value and effect sizes for the tests between the two conditions (HYP and MM) on outcomes. While the study was not powered to simultaneously test for the primary and secondary outcomes, it is reasonable to assume that the sample size of 80 participants per condition (determined to adequately power the primary hypotheses) will allow for reliable estimates of the effect sizes for secondary outcomes as well.

Longer-term effects of HYP and MM, relative to ED.

As part of our exploratory aims, we plan to assess the extent to which change in pain intensity, the primary outcome, is maintained at 3 and 6 months post-treatment, and to see if longer term changes in pain intensity differ between HYP and MM compared to ED. To assess this, we propose to use a Generalized Estimating Equations (GEE) approach, which accounts for the correlated nature of the data due to multiple observations of the same person over time. Response variables over time will be the change from pre-treatment to post-treatment, and pre-treatment to 3- and 6- months follow-ups, with intervention group and follow-up time as the main factors of interest (including a Group X Time interaction), and the pre-treatment value as the covariate. For the correlation matrix, we will assume an unstructured format, since there was no a priori reason to use a more structured matrix format. We will repeat these analyses for the secondary outcome measures mentioned above.

Mediation analyses.

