The goal of mediation analyses is to examine whether group assignment (determined by randomization at baseline) impacts the change in pain intensity (primary outcome) from baseline to post-treatment through indirect effects on the hypothesized mediators (measured midway

between baseline and post-treatment). Our potential mediators have been identified a priori and are shown in the table of measures (Table 4).

To evaluate the association between intervention type, potential mediating factors, and change in pain intensity, we will first run models with individual mediators to get unadjusted estimates and to estimate the degree of confounding in subsequent multivariate models. Per Hayes & Rockwood's 2017 recommendations, we will test multiple mediators in the same model, to more accurately reflect our theoretical understanding of parallel biological and psychological mediating processes, and to facilitate comparison of the size of indirect effects through different mediators. Mediators to be included in the model include change in EEG composite scores for theta, alpha, beta, and gamma bandwidths, pain acceptance, catastrophizing, mindfulness, therapeutic alliance, and skill practice. Also per the recommendations of Hayes and Rockwood (2017), we will compute bootstrap confidence intervals for the indirect effects. All mediation analyses will be done using PROCESS, a free downloadable add-on available for SPSS and SAS (the analysis packages we will use for the study's data analysis). PROCESS includes the computational code to generate a primary estimate for the mediation model which represents the indirect, or mediated effect, and allows for inclusion of moderator variables.

Our study is longitudinal and, in addition to posttreatment assessments, we have collected data at 3- and 6-months post-treatment on outcomes and all other variables (mediators and moderators). While the approach used in the PROCESS software can be somewhat adapted for longitudinal analysis, the most appropriate analysis would be longitudinal structural equations models, particularly latent growth models (e.g., Goldsmith et al. 2018). These models require specialized software such as AMOS or LISREL and are beyond the scope of our exploratory aims. If we are able to access such statistical resources in the future, however, we would like to leverage this dataset for these exploratory purposes.

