Additional moderator analyses. As in any study, we are interested in exploring whether the treatments have different effects at different levels of other variables, that is, if there are interactions between treatments and those variables (which then would be called moderators). In our study, we have 16 potential moderators (e.g., demographic variables, baseline beta activity, etc., see Table 4). Given the large number of potential moderators and their interactions with treatment, it would not be adequately statistically powerful nor easily interpretable to include all of them in a single model at once. On the other hand, 16 models with a single potential moderator would not give a realistic picture of how the moderation effects were acting in the population of interest. To address these concerns, we propose to first assess the correlations between the potential moderators. If two or more potential moderators are highly correlated, we are unlikely to enter them in the same model (due to collinearity) and if necessary will choose one of them (based on what is known about the variable, such as how reliable it is) to continue as a candidate.

This process might reduce the number of potential moderators in a way that uses both empirical support (correlations) and integrates our theoretical knowledge about the variables. Once the potential moderators have been winnowed to a smaller number, we will construct the models gradually, by including potential moderators and their interaction with treatment in a forward fashion (in the order of statistical significance). Hayes and Rockwood (2017) recommend use of the macro PROCESS for this, which writes the SPSS syntax for a specified model. Statistically significant Treatment Condition X Moderator interactions would suggest that the impact of the moderator variable on outcome differs as a function of treatment condition. In the absence of interaction, statistically significant main effects for the potential moderators would suggest that they might be associated with the outcome. Given the very large number of exploratory moderator analyses proposed, we will be very cautious in interpreting the results, and will use

these analyses only as a way of identifying potential moderators to examine more closely in future research.

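### The Aim 2 EEG regression leaves out baseline pain, and its EEG predictors are defined in two different ways

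*Combined protocol and SAP*

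**What the plan says.** D6x (Statistical Analyses, Aim 2) uses a linear regression with pre- to post-treatment pain change as the response. The explanatory variables are "Treatment Condition, absolute power of baseline theta, alpha, and (left frontal) gamma, and terms representing the interaction between treatment condition and each EEG bandwidth". The support criterion is "Significant Treatment Condition X Theta, Alpha, and Gamma interactions", with stated directions for the HYP and MM coefficients. Baseline pain is not listed.

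Other models of change in D6x do adjust for a baseline value:
- Aim 1 ANCOVA, same response: "treatment condition (HYP, MM, ED) as the explanatory variable and the baseline pain as a covariate".
- Secondary-outcome ANCOVAs: "the corresponding baseline value for each secondary outcome measure as a covariate", that is, each outcome's own baseline and not baseline pain.
- Longer-term GEE: change from pre-treatment, "and the pre-treatment value as the covariate".

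The mediation models ("To evaluate the association between intervention type, potential mediating factors, and change in pain intensity") and the additional moderator models (built "by including potential moderators and their interaction with treatment in a forward fashion") name no baseline pain covariate either. Table 4 lists only medical service use and medication use as covariates, so it does not supply the missing term.

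On the EEG predictors, D6t (Study Data, brain state) says the primary EEG analysis uses ratios of each band to total power over the whole brain. D6x uses absolute power, and the gamma term is left frontal.

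Hypothesis 2 (Précis and A2) adds: "Baseline brain activity will not be significantly associated with pain reduction following ED". The mediation text says mediators are measured midway through treatment, includes EEG change among them, and says mediators were also collected at 3 and 6 months. D1, Table 5 and Appendix 1 place EEG before and after treatment only.

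**The concern.** A change score still carries baseline pain, because people who start high tend to fall more. Leaving baseline pain out puts that variation into the residual and widens the standard errors of the treatment-by-EEG terms. Aim 2 is one of the trial's two aims, with its hypothesis labelled secondary. D6z sizes the trial for the primary hypothesis only. EEG is optional (D6j), so Aim 2 may have fewer than 240 participants. There is little precision to spare, and the missing variable is already collected.

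A second risk arises if baseline pain itself changes how well a treatment works and also correlates with EEG. EEG can then appear to be a moderator only because it stands in for pain.

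The two EEG definitions are a separate matter. Absolute and relative power are different predictors, and whole-brain gamma is not left frontal gamma. With both in the plan, the choice could be made after results are seen.

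**Working it through.** **The plan's own figure.** D6z gives 80 completers per arm for at least 80% power at SD 1 in a three-group ANOVA of change. For the smallest listed effects (ED 0.3, HYP 0.8, MM 0.6) the mean is 0.567 and the squared deviations sum to 0.1267. The noncentrality is 80 × 0.1267 / 1² = 10.13 on 2 and 237 df. Power is 81.6%, and 78 per arm reaches 80%. The figure reproduces, but it concerns Aim 1; no Aim 2 power is given.

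**Precision.** Let pre SD = 1, post SD = k and pre-post correlation = r, none of which the documents give.
- Residual variance of change without baseline: 1 + k² − 2rk.
- With baseline: k²(1 − r²).
- Ratio V = k²(1 − r²) / (1 + k² − 2rk). The extra sample for equal precision is 1/V − 1.

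| k | r = 0.4 | r = 0.7 |
|---|---|---|
| 1.0 | V 0.70, 43% more | V 0.85, 18% more |
| 1.2 | V 0.817, 22% more | V 0.966, 3% more |
| 1.3 | V 0.860, 16% more | V 0.991, 1% more |

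To use the plan's largest change SD of 1, take equal pre and post SD s, so that 2s²(1 − r) = 1 and r = 1 − 1/(2s²). With assumed s = 1.5, r = 0.778, V = 0.889 and the extra is 12%. With s = 2, r = 0.875, V = 0.9375 and the extra is 7%.

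**Power.** If the adjusted test has 80% power, unadjusted power is about Φ(2.80√V − 1.96). That is 65% at V = 0.70, 73% at V = 0.85, 75% at V = 0.889 and 77% at V = 0.9375. A simulation of the three-band model (3 × 80, 3,000 runs, HYP-versus-ED slope contrast, EEG-pain correlation 0.2) agrees. With equal SDs and r = 0.4 to 0.7 it gives 63%-72% unadjusted against 78%-79% adjusted. With k = 1.3 and r = 0.7, both are 78%-79%. The count of 3 × 80 is an upper figure because EEG is optional.

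**When the interaction test is valid.** Let the slope of post on baseline pain be β in every arm. Change then contains (1 − β) × baseline pain. Randomisation makes the relation of EEG to baseline pain the same in each arm, so this adds the same EEG slope everywhere and cancels from the interaction. Simulated type I error with a common slope is 4.1%-5.8%, with or without baseline pain.

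**When it is not.** If the slope differs by δ in HYP and EEG correlates ρ with baseline pain, the HYP-by-EEG coefficient shifts by about δρ. With δ = 0.3 and ρ = 0.3 (both assumed) this is 0.09. One simulation (r = 0.5, 240 participants, 3,000 runs, no EEG effect of its own) gave:

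| Model | Coefficient | SE | Rejects |
|---|---|---|---|
| No baseline pain | 0.093 | 0.171 | 8.9% |
| Baseline pain main effect | 0.089 | 0.143 | 9.5% |
| Plus baseline pain × treatment | −0.001 | 0.149 | 5.4% |

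Across repeat simulations the ranges were about 8%-9%, 8%-11% and 5%. The main effect shrinks the standard error but leaves the shift in place, so it does not help here.

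**ED slope.** In a one-band model with equal SDs, EEG-pain correlation 0.2-0.3 and no EEG role in change, the ED slope reaches p < 0.05 at these rates:
- EEG tracks observed baseline pain: 10%-31% unadjusted, about 5% adjusted.
- EEG tracks only stable pain: about 5% unadjusted, 12%-48% adjusted.

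Neither model is safe for that slope.

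**The case against.** The strongest reply is that the planned test is sound as it stands, and that the gain from adjustment is an efficiency preference on a secondary hypothesis for which the trial was not sized. The calculation closest to a figure in the plan gives only 7%-12% more participants. Much of this stands: the loss is modest on that reading and rests on assumed correlations throughout. It does not remove the point, because the variable is in hand and costs one degree of freedom, and the plan gives no reason for treating the same response differently in Aims 1 and 2.

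A reader might infer that omitting baseline pain makes the Aim 2 tests invalid. The documents do not support that. Invalidity needs baseline pain to modify a treatment effect and to correlate with EEG, and nothing in the plan says either holds. Even then EEG would be a real predictor of differential response, but only as a proxy for pain. Nor can validity be asserted without that condition.

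A reader might also infer that Aim 2 is the only model without baseline pain. It is not: the mediation and moderator texts do not name it, and the secondary-outcome ANCOVAs use their own baselines.

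On the ED prediction, it is fair to say that with ED as reference the model already estimates the ED slopes as its EEG main effects. What is missing is a rule for reading them, and a non-significant slope would not show absence of association.

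**Conclusion.** The point holds in two parts and should be acted on.

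First, baseline pain is absent from the Aim 2 regression. With a common baseline slope across arms, the consequence is lost precision only, equivalent to about 1%-43% more participants under assumed correlations of 0.4-0.7 and post SD of 1 to 1.3 times pre SD. Under assumed effect modification and correlation of 0.3 each, the interaction test rejects 8%-9% instead of 5%, and only baseline pain by treatment restores it.

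Second, D6t and D6x disagree on both the scale and the gamma region of the Aim 2 predictors. This needs no assumption. The hypothesis text and D6x agree with each other on left frontal gamma; the mismatch is with the measurement section.

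The ED slope and the mediation timing are minor reporting matters. Mediation is labelled exploratory, and the timing error does not touch the Aim 2 test. It would be wrong to conclude that adding baseline pain makes the ED slope unbiased.

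**What to change.** 1. Add baseline pain as a covariate to the Aim 2 regression. Pre-specify a sensitivity analysis that also includes baseline pain by treatment. The cost is one degree of freedom for the first and three in total for the second.
2. Before analysis, fix one EEG scale (absolute or relative power) and the region for each band for Aim 2. Make D6t and D6x agree, and report the other scale as a sensitivity analysis.
3. Minor: report the ED-arm EEG slopes with confidence intervals, with and without baseline pain, and do not read a non-significant slope as no association.
4. Minor: correct the mediation text to say that EEG is recorded only before and after treatment, and describe any EEG mediation result as concurrent with pain change.

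All of this is analysis-plan wording and reporting. The variables are already collected, and visits, sample size and data collection do not change.
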